Depression is a common comorbidity in adults with DS which is likely underestimated in naturalistic prevalence studies; reported prevalence rates range from 6-18% [9–13]. A recent study which included 605 individuals with DS from England and Wales demonstrated that 12.4% of younger adults (16–35 years) and 18.4% of older adults (≥ 36 years) had a lifetime history of depression based on medical record review [13]. Females and males with DS had a four- and five-fold increased risk of depression respectively, compared to the general United Kingdom adult population [13]. In a separate longitudinal cohort study, 134 adolescents and adults with DS (≥ 16 years) participated in a detailed psychiatric assessment with psychiatrists who had expertise in DS at baseline and two years later [12]. The two-year incidence of a major depressive episode in this study was 5.2% [12]. Adults with DS have several unique risk factors for developing depression compared to the general population including cognitive impairment [14], reduced serotonin brain tissue concentration in post-mortem studies [15], high prevalence of thyroid disorders [3], and significant emotional stressors related to the transition to adulthood and the accompanying loss of school-based programming and services.

Depression is often underrecognized and undertreated in adults with DS. There are several diagnostic challenges related to the inherent communicative and cognitive limitations. While the clinical characteristics of depression in individuals with DS are often similar to those seen in the general population including sad mood, diminished experience of pleasure, decreased appetite and weight loss, social withdrawal, reduced speech, low energy, and psychomotor slowing [6], individuals with DS may have difficulty expressing depressive thoughts such as of guilt, worthlessness, self-deprecation, or thoughts of suicide [10]. These clinical features may necessitate taking into account behavioral observations and caregiver report rather than strict application of diagnostic criteria. A retrospective study assessing the clinical features of depression in DS reported that when strict Diagnostic and Statistical Manual of Mental Disorders, Third Edition (DSM-III-R) criteria were applied, only 50% of depressive episodes diagnosed by expert clinicians met full criteria [10]. This study also demonstrated that depression was frequently misdiagnosed as dementia in individuals with DS and therefore left untreated.

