The same IRB-approved accommodations for out of state patients our group is using in a similar open-label drug trial of buspirone for anxiety in Williams syndrome (Protocol #2021P000376) will be utilized for this study. All participants will be seen for either an in-person or virtual visit for the screen and baseline visits, the primary purpose of which are to establish care and determine the diagnosis and treatment plan. The prescription of fluoxetine will occur at the time of the baseline visit. In accordance with the Mass General Brigham Virtual Visit Procedures (applicable as of April 1, 2021), virtual visits will only be conducted with patients who are located in New England and Florida at the time of the visit and only by attending physicians who are licensed in those states. In accordance with the "FAQs for Mass General Brigham Clinicians: Changes to Procedures for Out of State Virtual Visits" (July 15, 2021) guidelines, the weeks 2, 4, 6, 8, 10, 12, and 16 visits will be conducted as "Customary telephone calls." These visits will consist of brief, logistical conversations with the purpose of communicating with subjects, adjusting prescriptions, and ensuring continuity of care by reviewing adverse effects and concomitant treatments/medications. If at any time during a "Customary telephone call" the study team learns of information concerning for new symptoms that are inconsistent with the diagnosis established during the baseline visit, symptoms that warrant a different treatment plan, or any other reason that in the attending physician's judgment that warrants a medical visit, the subject will be referred for either local clinical care within their state or offered an in-person visit in Massachusetts.

**In person regular and endpoint visits will be offered for all participants who are able to attend and participate in study procedures.*

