2. **Current or previous diagnosis of dementia, or use of medication to treat dementia.** Given the potential overlap between depression and dementia symptoms, we want to ensure we are administering fluoxetine to patients with a diagnosis of depression.

3. **Presence of any past or present conditions that would make treatment with fluoxetine unsafe.** This includes allergy to fluoxetine, liver or kidney disease, unstable heart disease, and/or pregnancy (or being sexually active without using acceptable methods to prevent pregnancy).
4. **Use of selective serotonin reuptake inhibitors (SSRIs), serotonin norepinephrine reuptake inhibitors (SNRIs), tricyclic antidepressants (TCAs), monoamine oxidase inhibitors (MAOIs), bupropion, mirtazapine, antipsychotics, lithium, valproic acid, or carbamazepine.** Subjects will need to be off these classes of medications for at least 5 elimination half-lives prior to beginning the trial.
5. **Use of other psychotropic medications which are ineffective, poorly tolerated, or sub-optimal in terms of dose.** A board-certified psychiatrist will assess any other psychotropic medications being used and determine whether they are effective, tolerated, and optimal in terms of dose. If medications are ineffective, poorly tolerated, or sub-optimal in terms of dose, the study psychiatrist will work with the subject and his/her treatment team to either taper or optimize the dose of psychotropic medications prior to study enrollment. Concurrent use of a psychotropic medication (other than SSRIs, SNRIs, TCAs, MAOIs, bupropion, mirtazapine, antipsychotics, lithium, valproic acid, or carbamazepine) will be allowed if the dose has been stable for 30 days and if they meet the criteria of effectiveness, tolerability, and dose.
6. **Previous adequate trial of fluoxetine.** An adequate trial will be defined as a total daily dose of ≥ 30 mg for at least 4 weeks. In addition, subjects who developed significant adverse effects during a trial of fluoxetine at any dose or duration will be excluded.
7. **Severe or profound intellectual disability based on clinical assessment and review of standardized assessment of cognitive skills.** Participants determined to have severe or profound intellectual disability will be excluded.
8. **Use of medications that pose a clinically significant risk of a drug-drug interaction with fluoxetine.**

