All subjects will have a baseline psychiatric diagnostic evaluation done to gather a thorough developmental, medical, and psychiatric history, as well as a mental status examination, and vital signs will be obtained for subjects evaluated in the clinic if subject cooperation allows. This will be determined by a board-certified psychiatrist experienced in the care of adults with developmental disabilities. Examples of lack of cooperation due to emotional dysregulation include refusal to participate, repeated requests for a break, and verbalizations of distress. Lack of cooperation may occur and is expected occasionally in this population. In visits where subject measures cannot be completed, measures from the caregiver will be collected only. In clinical care it is standard for caregivers to be the primary reporters of response to medication, therefore it is still valuable to collect non-primary outcome measures from the caregiver. Lack of cooperation would only become withdrawal of assent if behaviors stated in the assent section occur, for example regularly refusing to take the medication. If the visits are conducted remotely, not all vital signs will be obtained. The medical history will be aimed at ruling out other medical conditions that could exacerbate depression or behavioral symptoms (e.g., chronic gastrointestinal disease, obstructive sleep apnea, thyroid disease). The following standardized scales and testing may also be conducted. If cognitive testing has been completed within the past five years, these medical records may be requested and reviewed to inform study eligibility criteria.

- 1. Stanford-Binet Intelligence Scales, Fifth Edition (SB-5)** [33]. The SB-5 may be used to calculate an abbreviated battery IQ. The abbreviated IQ was chosen to limit subject burden given that a number of other measures will be conducted at screening.
- 2. The Wechsler Abbreviated Scale of Intelligence, Second Edition (WASI-II)** [34]. The WASI-II can also be administered remotely and will be used for subjects depending on age and ability.
- 3. Developmental Profile, Fourth Edition (DP-4)** [35]. If patients are unable to obtain a valid score on the SB-5 ABIQ or WASI-II due to constraints of a virtual visit or significantly delayed cognitive skills, the Cognitive and Adaptive Behavior subscales of the Developmental Profile (DP-4) Parent/Caregiver Interview Form may be administered. DP-4 scores will require a minimum age-equivalency cutoff of 24 months.

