We will estimate percentage response to fluoxetine treatment, and corresponding 95% confidence interval, for adults with DS using the proportion of participants with CGI-I scores ≤ 2 at 16 weeks. Participants with missing 16-week CGI-I scores will be treated as non-responders. Frequency of all side effects and adverse events and corresponding 95% confidence intervals will be tabulated. Percent tolerating treatment and corresponding 95% confidence intervals will be estimated using the proportion of participants who did not withdraw from the study before 16 weeks due to reasons other than side effects or an adverse event who discontinue treatment due to side effects or an adverse event. We will also use the 16-week study retention rate and corresponding 95% confidence interval, calculated as the proportion of the participants enrolling in the study who remain in the study for 16 weeks, as a measure of feasibility.

To estimate changes in depression scale scores, including the MADRS, HAM-D, GDS-LD, and GDS-CS, we will use repeated measures linear regression models, as implemented in PROC MIXED in SAS and fit using REML estimation, with repeated measurements of clinical scores as outcomes and time, in categories, as the predictor. We will allow unstructured covariance between repeated measurements from the same participant. Our primary interest will be only in the difference between baseline and week 16 scores, but all observed scores will be included as outcomes, given that partially observed scores may be informative for estimation. We will obtain an estimate of 16-week change and corresponding 95% confidence interval using a contrast of the week 16 and baseline model parameters. Sensitivity to change will be compared between scales using standardized effect sizes, calculated using the model-estimated 16-week change in each outcome divided by 1) the model-estimated standard deviation of the outcome at baseline and 2) the model-estimated standard deviation of the change score. Spearman correlations will quantify the strength of association between change in depression scale score and CGI-I ratings among those with observed 16-week data. We will also tabulate and compare the percent of item-level missing data for each scale.

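### Other antidepressants and psychotropics are restricted only at entry, so a participant who improves after starting or increasing one during the 16 weeks counts as a fluoxetine responder

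*Combined protocol and SAP*

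**What the plan says.** Section 4, exclusion 4, lists SSRIs, SNRIs, TCAs, MAOIs, bupropion, mirtazapine, antipsychotics, lithium, valproic acid and carbamazepine. Candidates must be "off these classes of medications for at least 5 elimination half-lives prior to beginning the trial". Exclusion 5 deals with all other psychotropics. If one is judged ineffective, poorly tolerated or sub-optimal in dose, the study psychiatrist will work with the treatment team to "either taper or optimize the dose of psychotropic medications prior to study enrollment". Otherwise its use "will be allowed if the dose has been stable for 30 days and if they meet the criteria of effectiveness, tolerability, and dose". Both rules are tied to the start of the trial.

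Concomitant treatments and medications are marked at every visit in Table 1 (Section 6), and Section 3 describes the telephone contacts as "ensuring continuity of care by reviewing adverse effects and concomitant treatments/medications".

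The primary outcome (Section 6, Outcome Measures, item 5) is the percentage with a week-16 CGI-I of 1 or 2. Aim 1A (Section 2) requires an observed rate of at least 35%. The Statistical Analysis Plan in Section 9 contains one override of the rating: "Participants with missing 16-week CGI-I scores will be treated as non-responders". It makes no use of the concomitant-treatment record.

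**The concern.** The effectiveness criterion is meant to describe response to fluoxetine. A participant who starts a second antidepressant at week 6, or has a permitted psychotropic increased at week 8, and is rated much improved at week 16 is scored exactly like one who took fluoxetine alone. The bias has a known direction, because such changes can only add to the count of responders credited to fluoxetine.

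The protocol accepts the principle. Exclusion 1 bars certain primary diagnoses because their treatment could confound the study's assessments. The same confounding, arising after entry, has no rule.

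The criterion is a count in a small single-arm study, so a few such participants can decide it. Its result is to inform whether a larger placebo-controlled trial follows.

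**Working it through.** **Inputs**
- Rule: observed response of at least 35% (Section 2, Aim 1A).
- Sample size in the power statement: 20 (Section 9). Planned enrolment: 25 (Section 4).
- Unfavourable and favourable true rates: 20% and 44% (Section 9).
- Responders needed: 0.35 × 20 = 7; 0.35 × 25 = 8.75, so 9.
- Number of participants with a background drug change: not in the documents; assumed below.

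**Step 1. The plan's own figures.** With X binomial(20, p):
- p = 0.20: P(X ≥ 7) = 0.087, so P(X < 7) = 0.913. This agrees with the stated chance of more than 90%.
- p = 0.44: P(X ≥ 7) = 0.850. The plan states more than 90%, which this does not reproduce. That is a separate matter; 0.850 is the reference used in Step 3.

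**Step 2. Effect of misattributed responders.** Suppose k participants are rated 1 or 2 only because of another drug change, and the other n − k respond with probability 0.20. The rule is then met with probability P(Y ≥ r − k), where Y is binomial(n − k, 0.20) and r is the number needed.

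| k | n = 20, r = 7 | n = 25, r = 9 |
|---|---|---|
| 0 | P(Y ≥ 7 of 20) = 0.087 | P(Y ≥ 9 of 25) = 0.047 |
| 1 | P(Y ≥ 6 of 19) = 0.163 | P(Y ≥ 8 of 24) = 0.089 |
| 2 | P(Y ≥ 5 of 18) = 0.284 | P(Y ≥ 7 of 23) = 0.160 |
| 3 | P(Y ≥ 4 of 17) = 0.451 | P(Y ≥ 6 of 22) = 0.267 |

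At 20 participants, one such responder takes the protection at a true 20% from 0.913 to 1 − 0.163 = 0.837, below the stated 90%. At 25, one leaves it at 1 − 0.089 = 0.911, and two take it to 1 − 0.160 = 0.840.

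**Step 3. Cost of scoring such changes as non-response.** If a share c of participants has a qualifying change, independently of response, the counted response probability is p × (1 − c).

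| c | 0.44 × (1 − c) | Chance of meeting rule, n = 20 | n = 25 |
|---|---|---|---|
| 0 | 0.440 | 0.850 | 0.843 |
| 5% | 0.418 | 0.799 | 0.784 |
| 10% | 0.396 | 0.738 | 0.713 |
| 15% | 0.374 | 0.668 | 0.631 |

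At a true 20% and n = 20, the chance of meeting the rule falls from 0.087 to 0.069, 0.054 and 0.041 for the same three shares.

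**The case against.** The strongest reply is that the entry rules already remove most of the foreseeable reason for change: a permitted psychotropic must be judged effective, tolerated and optimal in dose before enrolment. This stands as a reason to expect few changes. It does not say how one is scored when it occurs. Nor does reading exclusion 4 as a ban that runs through the trial settle it: the text ties that ban to the start and gives no analysis consequence for a breach. Section 3 provides for referral when symptoms call for a different treatment plan, without saying that the participant leaves the study or the analysis.

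Second, the trial is open-label, uncontrolled and claims only preliminary evidence. Spontaneous improvement, regression to the mean after entry at a MADRS of 20 or more, and expectancy would remain even if no other treatment changed. This is right. A reader might infer that stable background care is the only thing protecting attribution to fluoxetine; it is one safeguard among several that a single-arm study lacks or has only in part.

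Third, a reader might infer that the CGI cannot separate causes because it is said to reflect all factors. In Section 6 that phrase concerns sources of information (parent report, parent-rated and clinician-rated measures). A trained clinician could discount another treatment's effect. What can be said is that no instruction asks for this.

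Fourth, a reader might infer that someone whose thyroid disease or sleep apnoea is discovered at work-up will enrol while its treatment begins. The documents do not say so. "The medical history will be aimed at ruling out other medical conditions that could exacerbate depression or behavioral symptoms", Table 1 places that history at Screen, and Screen and Baseline may be combined only when eligibility is clear. The supportable remark is narrower: no consequence of a positive finding is stated. Section 1 does cite a "high prevalence of thyroid disorders" among the depression risk factors in Down syndrome. These conditions are described as common in this population, so scoring a routine change in their treatment as failure could discard genuine fluoxetine responders.

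**Conclusion.** The point holds for other antidepressants and psychotropics. The entry rules stop at the start of treatment, the response rule ignores what is added afterwards, and the visit log that would identify it goes unused. The resulting count is biased toward meeting the 35% criterion.

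The size is conditional. The illustration at 20 participants assumes a true response of 20% and a fixed number of misattributed responders; the documents support no particular number. If no such changes occur, the result is unaffected.

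The documents do not support extending the same primary scoring to psychotherapy, thyroid or sleep-apnoea treatment. For these, a planned sensitivity analysis is proportionate. Whether background care should be held constant during the trial is a clinical decision on which this point takes no position.

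**What to change.** Change the SAP only; eligibility and care stay as they are.

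1. For the 35% criterion, score as a non-responder any participant who, after baseline and before the week-16 rating, started a medication in the exclusion-4 classes (other than study fluoxetine) or started or increased any other psychotropic. Report alongside it the rate with these participants counted as rated, both with Wilson intervals as already planned.
2. For new or changed psychotherapy, thyroid treatment or sleep-apnoea treatment, leave the primary scoring unchanged and report response with and without those participants as a sensitivity analysis.
3. Report the number of participants in each group, taken from the concomitant-treatment and medication records in Table 1.

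No new data are needed. The cost is a less favourable response rate and a lower chance of meeting the criterion when fluoxetine works. At a true 44% and 20 participants this chance falls from 0.85 to 0.80 if 5% have a qualifying change independent of response, and to 0.74 if 10% do. The loss grows with the number affected, which is why item 1 is confined to antidepressants and psychotropics and both rates are reported.

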6. STUDY PROCEDURES

Screen Visit:

The purpose of the *screen visit* is to ensure participants meet the eligibility criteria as defined above in Subject Selection.

In order to distinguish subjects who should be excluded due to profound intellectual disability from subjects who are not able to provide assent, the presence of severe or profound intellectual disability will be determined based on a clinical evaluation by a board-certified psychiatrist and psychologist (both experienced in the care of and conducting research involving adults with developmental disabilities) which takes into account a clinical assessment, review of cognitive testing (if available), and the clinically appropriate use of standardized scales (Stanford-Binet Intelligence Scales Weschler Abbreviated Scale of Intelligence, Second Edition; or Developmental Profile, Fourth Edition).

If it is clear that participants meet all eligibility criteria, the *Screen* and *Baseline* visits may be combined into a single visit during which the Montgomery-Asberg Depression Rating Scale (MADRS) would only be conducted once.

Baseline Characterization:

All subjects will have a baseline psychiatric diagnostic evaluation done to gather a thorough developmental, medical, and psychiatric history, as well as a mental status examination, and vital signs will be obtained for subjects evaluated in the clinic if subject cooperation allows. This will be determined by a board-certified psychiatrist experienced in the care of adults with developmental disabilities. Examples of lack of cooperation due to emotional dysregulation include refusal to participate, repeated requests for a break, and verbalizations of distress. Lack of cooperation may occur and is expected occasionally in this population. In visits where subject measures cannot be completed, measures from the caregiver will be collected only. In clinical care it is standard for caregivers to be the primary reporters of response to medication, therefore it is still valuable to collect non-primary outcome measures from the caregiver. Lack of cooperation would only become withdrawal of assent if behaviors stated in the assent section occur, for example regularly refusing to take the medication. If the visits are conducted remotely, not all vital signs will be obtained. The medical history will be aimed at ruling out other medical conditions that could exacerbate depression or behavioral symptoms (e.g., chronic gastrointestinal disease, obstructive sleep apnea, thyroid disease). The following standardized scales and testing may also be conducted. If cognitive testing has been completed within the past five years, these medical records may be requested and reviewed to inform study eligibility criteria.

- 1. Stanford-Binet Intelligence Scales, Fifth Edition (SB-5)** [33]. The SB-5 may be used to calculate an abbreviated battery IQ. The abbreviated IQ was chosen to limit subject burden given that a number of other measures will be conducted at screening.
- 2. The Wechsler Abbreviated Scale of Intelligence, Second Edition (WASI-II)** [34]. The WASI-II can also be administered remotely and will be used for subjects depending on age and ability.
- 3. Developmental Profile, Fourth Edition (DP-4)** [35]. If patients are unable to obtain a valid score on the SB-5 ABIQ or WASI-II due to constraints of a virtual visit or significantly delayed cognitive skills, the Cognitive and Adaptive Behavior subscales of the Developmental Profile (DP-4) Parent/Caregiver Interview Form may be administered. DP-4 scores will require a minimum age-equivalency cutoff of 24 months.

Fluoxetine Treatment:

Subjects will receive fluoxetine 5 mg each morning at the start of the trial. The dose will be flexibly increased by 5 mg every two weeks depending on effectiveness and tolerability. During the first 12 weeks, patients will be seen monthly with additional telephone visits conducted in between clinical visits for additional monitoring of adverse effects and for dosing adjustment as necessary. The optimal dose (between 5-30 mg per day), based on effectiveness and tolerability, will be reached by week 12 of treatment. A final visit will be conducted at week 16. At the end of the 16-week trial, participants will be referred for ongoing care either at the Lurie Center or locally, per their preference. The decision to continue or discontinue fluoxetine at the end of the trial will be made collectively by the research psychiatrist, the patient, and their family.

The minimum starting dose will be 5 mg and the maximum total daily dose will be 30 mg. If up titration is not tolerated, no more than one repeat attempt at up titration will be made. The decision to attempt a repeat up titration will be made by the research psychiatrist taking into account the full clinical picture of probable risks and benefits as well as the patient/family's preference. Fluoxetine is prepared in 10 mg tablets as well as a liquid formulation and will be dosed daily (see example of dosing schedule below).

Example Dosing Schedule	
	Dose (mg)
Weeks 1 & 2	5
Weeks 3 & 4	10
Weeks 5 & 6	15
Weeks 7 & 8	20
Weeks 9 & 10	25
Weeks 11 & 12	30

Weeks 13-16	Stable dose for last 4 weeks of study
* The schedule is a guide and may be adjusted depending on tolerability and effectiveness.	

The rationale for this dosing schedule is based upon pilot data our group obtained. A retrospective chart review study from our clinic included 11 adults with DS and depression who were treated with a selective serotonin reuptake inhibitor (most commonly fluoxetine). The overall response rate was 82%. The mean starting dose for fluoxetine was 4.9 mg per day and the mean maximal dose was 25.5 mg per day. [20]

Study medication will be prescribed to participants by the study's psychiatrist and the cost will be billed to their insurance following the same procedures as routine clinical care. The Lurie Center has clinical infrastructure including Medical Assistants and Nursing Staff to assist with Prior Authorizations as needed. We plan to prescribe a one-month supply of medication to mimic real-world clinical practice but can prescribe up to a three-month supply if required by insurance.

Outcome Measures:

1. **Montgomery-Asberg Depression Rating Scale (MADRS).** Change in MADRS total score between baseline and 16 weeks will be a secondary outcome measure. The MADRS is one of the most frequently used outcome measures in antidepressant efficacy trials and was developed to assess change in depressive symptoms after treatment with antidepressants [27]. The scale is clinician-rated and consists of 10 items, each rated on a 0-6 scale and summed to determine the total score. A total score of 7-19 is indicative of mild depression, 20-34 of moderate depression, 35-59 of severe depression, and 60 or greater of very severe depression. The MADRS will be conducted at screening, baseline, and each follow-up visit.
2. **Hamilton Depression Rating Scale (HAM-D).** Change in HAM-D total score between baseline and 16 weeks will be a secondary outcome measure. The 17-item HAM-D is one of the most frequently utilized outcomes measures in clinical trials for depression and is a clinician-rated scale with scores based on clinical interview and family report [28]. It addresses both somatic and psychological symptoms of depression. Items are rated on either a 5-point scale (0 to 4) or 3-point scale (0 to 2), where higher scores represent increasing severity of depression. The scores of the 17 items are summed to obtain a total score. The HAM-D will be optional and possibly conducted at baseline and each follow-up visit if time allows.
3. **Glasgow Depression Scale for people with a Learning Disability (GDS-LD) and Carer Supplement (GDS-CS).** Change in GDS-LD total score and change in GDS-CS total score between baseline and 16 weeks will each be secondary outcome measures. The GDS-LD and GDS-CS were developed to describe and quantify depressive symptoms in adults with mild-to-moderate learning disabilities [29]. The GDS-LD consists of 20 items scored from 0 to 2. The GDS-CS consists of 16 items scored from 0 to 2. The 20 and 16 item scores are summed to obtain GDS-LD and GDS-CS total scores respectively. Higher scores are indicative of more severe depression. The GDS-LD and GDS-CS will be conducted at baseline and each follow-up visit. The GDS-LD and GDS-CS will be secondary outcome measures.
4. **Pittsburgh Sleep Quality Index (PSQI).** Change in PSQI total score between baseline and 16 weeks will be an exploratory outcome measure. The PSQI is a self-rated 19-item questionnaire which assesses sleep quality and disturbances over a one-month time interval [30]. It will be used to assess the sleep quality of study participants by parent/caregiver report.
5. **Clinical Global Impressions (CGI).** The percentage of subjects who respond to treatment, with response defined as a 16-week CGI-I rating of 1 or 2, will be the primary outcome measure. A trained clinician will perform the CGI. The CGI is designed to take into account all factors to arrive at an assessment of symptom severity and response to treatment, including parent report, parent-rated measures, and clinician-rated measures (as described below) [31]. The CGI Severity (CGI-S) item is rated on a scale from 1 to 7 (1 = normal, not at all ill; 2 = borderline ill; 3 = mildly ill; 4 = moderately ill; 5 = markedly ill; 6 = severely ill; 7 = among the most extremely ill patients). The CGI Global Improvement (CGI-I) item is also rated from 1 to 7 (1 = very much improved; 2 = much improved; 3 =

minimally improved; 4 = no change; 5 = minimally worse; 6 = much worse; 7 = very much worse). Clinically meaningful improvement will be defined as a CGI-I rating of 1 or 2. The CGI-S will be conducted at screen, baseline and the last follow-up visit. The CGI-I will be conducted at each follow-up visit.

Safety Monitoring:

Participants will be monitored for possible pregnancy throughout the study. If a participant is of childbearing potential, a urine pregnancy test will be obtained at Screen. A positive result on a urine pregnancy test will then be confirmed via a blood pregnancy test, and a positive result on a blood pregnancy test will exclude them from study participation. We will continue to assess for pregnancy at all monthly clinic visits by asking participants if they are sexually active and if they are using contraception. Participants of childbearing potential who are sexually active and are not using an approved contraception method will be asked to complete a urine pregnancy test. A positive result on a urine pregnancy test will then be confirmed via a blood pregnancy test, and a positive result on a blood pregnancy test will exclude them from study participation.

Adverse events will be collected via a structured side effect rating scale completed with the participant and their primary caregiver. This will include a list of side-effects that have been reported with fluoxetine at a rate greater than 10% including sexual dysfunction, anorexia, diarrhea, nausea, dry mouth, anxiety, drowsiness, headache, insomnia, yawning, asthenia, tremor, and pharyngitis. Each of these side effects plus any additional complaints will be rated at baseline on a 4-point scale by the caregiver as follows: 0 = none; 1 = mild; 2 = moderate; 3 = severe. This scale is similar to that used by the RUPP Autism Network. Suicidality will be assessed at each visit by directly asking the subject (when verbal skills are sufficient) and the caregiver about any thoughts or behaviors that directly or indirectly might indicate suicidality (e.g., morbid thoughts, self-injury, statements about life being not worth living), when indicated by positive responses. At baseline, if suicidality is endorsed, the Columbia-Suicide Severity Rating Scale (C-SSRS) will be administered per the instructions at www.cssrs.columbia/ed/clinical_trials.html. The C-SSRS will also be administered at each subsequent visit following the first report of suicidality. Subjects and caregivers will also have information on how to contact the on-call physician from our practice group who provides coverage 24 hours/day and 365 days/year. Physicians taking call are familiar with research protocols and can contact the principal investigator at any time.

All adverse events picked up on the rating scale as new will be recorded by the physician. The physician will also ask about any visits to the doctor, new medication use (e.g. OTC cold medicine), or any other complaints, in order to be confident that most adverse events are uncovered. The physician will keep a running log of adverse events that will record the date of onset, date of resolution, seriousness, severity, and relationship to study intervention (e.g., definite, probable, possible, remote, or none) as well as whether the adverse event led to a change in study intervention or other treatment.

A physician will review vital signs as they become available. All significant adverse events as well as the progress of the study will be reviewed and discussed in detail at the biannual meetings of the Lurie Center Data and Safety Monitoring Board (DSMB). The DSMB includes rotating members of the Lurie Center including pediatricians, pediatric and adult neurologists, pediatric and adult psychiatrists, and independent members outside the Lurie Center.

If at any time during the course of the study, the DSMB judges that the risk to subjects outweighs the potential benefits, the DSMB shall have the discretion and responsibility to recommend that the study be terminated.

Schedule of Measures:

Table 1. Schedule of Measures		Treatment Phase
-------------------------------	--	-----------------

Mass General Brigham Institutional Review Board
Intervention/Interaction Detailed Protocol

Measure	#Screen ^^	#Baseline ^^^	Week 2^	Week 4^^^	Week 6^	Week 8^^^	Week 10^	Week 12^^^	Week 16^^^
Parent Ratings [1]									
Demographics	X								
SCID-5 [2]	X								
MADRS [3]	X	X		X		X		X	X
HAM-D [4] (optional)		X		X		X		X	X
GDS-CS [5]		X		X		X		X	X
PSQI [6]		X							X
Subject Assessments									
Vital Signs, Height, Weight (optional for remote visits)	X								X
Urine Pregnancy Test [7]	X								
Pregnancy Assessment				X		X		X	X
MADRS**	X	X		X		X		X	X
HAM-D** (optional)		X		X		X		X	X
GDS-LD**		X		X		X		X	X
Stanford-Binet-5 (SB-5) or other cognitive assessment	X								
Treating Clinician									
DS Diagnosis [8]	X								
Diagnostic Exam including medical/psychiatric history	X								
Health/Behavior Review	X								
Adverse Effects Review		X	X	X	X	X	X	X	X
CGI-Severity [9]	X	X							X
CGI-Improvement [10]				X		X		X	X
Suicide Assessment [11] / C-SSRS [12]	X	X	X	X	X	X	X	X	X
Concomitant Treatments	X	X	X	X	X	X	X	X	X
Concomitant Medications	X	X	X	X	X	X	X	X	X

#Screen and Baseline Visits may be combined into a single visit if subject clearly meets eligibility criteria.
^Telephone Visit; ^^In clinic; ^^^In clinic, Zoom, or telephone; **Administered when emotional regulation, cognitive, and communicative abilities allow; [1] Parent or primary caretaker ratings; [2] SCID-5 = Structured Clinical Interview for DSM-5; [3] MADRS = Montgomery-Asberg Depression Rating Scale; [4] HAM-D = Hamilton Depression Rating Scale; [5] GDS-CS = Glasgow Depression Scale for people with a Learning Disability Carer Supplement; [6] PSQI = Pittsburgh Sleep Quality Index; [7] Females of child-bearing potential only; [8] genetic testing or clinical diagnosis; [9] CGI-S = Clinical Global Impression for Severity; [10] CGI-I = Clinical Global Impression for Improvement; [11] Suicide Assessment included in Adverse Effect Review; [12] Columbia-Suicide Severity Rating Scale (C-SSRS) will only be administered to participant and/or parent if any positive suicidal ideation is reported on Health/Behavior Review (screen) or Adverse Effects Review (baseline and all subsequent visits). Each visit following the first report of suicidal ideation will include the administration of the C-SSRS.

Drug Compliance

Families will be asked to return drug diaries within 5 business days of the scheduled Week 2, 4, 6, 8, 10, 12, and 16 visits. The study coordinator and/or PI will calculate drug compliance based on the number of missed doses between visits. Adequate compliance will be defined as $\geq 70\%$ of doses. If compliance falls

below this threshold and/or drug diaries are not returned, the subject may be discontinued from the study, per PI discretion.

7. Risks and Discomforts

Overall, the risk to the subjects in this research are essentially no different from those that would exist in standard clinical practice, but the research proposed offers considerable promise in improving our understanding of the treatment of depression in individuals with Down syndrome. Foreseeable risks and discomforts include:

Drug-free washout interval

Withdrawal of a medication prior to the study will only be pursued in cases for which the current medication is not effective or is causing intolerable side effects. In collaboration with the prescribing clinician, the medication will be gradually tapered according to best clinical practices with close monitoring for symptom worsening.

Fluoxetine Treatment

Fluoxetine, an SSRI, has been well tolerated in children, adolescents, and adults. Common adverse reactions (>10%) include, asthenia, nausea, diarrhea, insomnia, nervousness, anxiety, and somnolence. Less common adverse reactions (<10%) include flu symptoms, decreased appetite, dry mouth, dyspepsia, constipation, dizziness, tremor, sweating, fever, vasodilation, flatulence, vomiting, weight loss, decreased libido, abnormal thinking, yawning, rash, pruritis, and abnormal vision. Very rarely, SSRIs may increase the risk of bleeding, a mixed/manic mood episode, suicidal thoughts, and/or QT prolongation. There is also the rare but potential risk of serotonin syndrome. If discontinued abruptly, fluoxetine discontinuation syndrome including flu-like symptoms, insomnia, nausea, balance problems, sensory disturbances, and hyperarousal may occur.

We will assess for these symptoms at all phone, video, and in-person visits. Any side effects will be closely monitored and recorded. In order to manage a side effect or suspected adverse event, the treating clinician is free to delay a scheduled increase or reduce the dose of the study medication. The dose schedules described above are guides only.

Fluoxetine has a half-life of 4 to 6 days. No specific laboratory monitoring is recommended with fluoxetine treatment.

Allergic Reactions

An allergic reaction can occur. Allergic reactions can be mild or serious and can even result in death. Common symptoms of an allergic reaction are rash, itching, skin problems, swelling of the face and throat, or trouble breathing. Participants will be instructed to call the study doctor immediately if they suspect they are having an allergic reaction. Participants will also be instructed to call 911 immediately and get medical assistance if they are having trouble breathing.

Risks to an Embryo or Fetus, or to a Breastfeeding Infant

